4.9.1.2 Deaths

The following deaths summaries will be generated on the all-treated population.

- Number (%) of patients who died during the study and reasons for death
- Number (%) of patients who died within 15 weeks after the last dose of study drug (excluding those who died after taking any subsequent anticancer therapy/procedure) and reasons for death

Listing of deaths will be provided.

4.9.2 Laboratory Data

Laboratory data of hematology, chemistry will be summarized for the raw data and the change from baseline value at each scheduled assessment. Descriptive statistics (mean, standard deviation, median, and range) will be calculated for the actual data and for their changes from baseline at each scheduled assessment.

All results will be graded according to CTCAE version 5.0. Shift tables will summarize the shift from baseline grade to maximum post-baseline CTCAE grade.

Summaries by visit will include data from scheduled assessments, and all data will be reported according to the nominal visit date for which it was recorded. Unscheduled data will be included in “worst case post-baseline” summaries, which will capture a worst case across all scheduled and unscheduled visits after the first dose of study treatment.

All laboratory data, including urinalysis and serology, will be listed.

4.9.3 Electrocardiogram Data

Electrocardiogram (ECG) parameters (e.g., corrected QT interval [QTc] in ms) will not be converted or derived, but will be reported as provided by investigational sites.

Descriptive statistics (mean, standard deviation, median and range) will be calculated for the raw data and for their changes from baseline at each scheduled assessment.

The following abnormal QTcF will be reported by a frequency table:

At any post-baseline with absolute value

>450 - <=480 ms
>480 - <=500 ms
> 500 ms

Change from Baseline

>30 – <=60 ms
>60 ms

All ECG data will be listed, both for quantitative data and for overall impression.

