7.4.7 Electrocardiograms

One 12-lead electrocardiogram (ECG) will be performed at screening as per SoE ([Table 2](#)). The ECG will be performed after the patient is resting for at least 5 minutes. Additional ECG assessments may be performed as clinically indicated.

Assessments will include determination of heart rate and rhythm and the PR, QRS, QT, and QTcF intervals.

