9.8.3 Additional Safety Assessments

The results of scheduled assessments of vital signs, physical examinations, ECOG performance status, and 12-lead ECGs will be summarized. All data will be reported according to the nominal visit date for which it was recorded (i.e., no visit windows will be applied). Unscheduled data will be included in “worst case” summaries, which will capture a worst case across all scheduled and unscheduled visits after the first dose of study drug. All data will be listed. Further details will be provided in the SAP.

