3.4 Modifications to the statistical section of the protocol

Not applicable

4 Statistical Methods

All analyses will use SAS® version 9.4 or higher.

Categorical data will be presented using counts and percentages, with the number of patients in the analysis population as the denominator for percentages. Percentages will be rounded to 1 decimal place and not be displayed for zero counts.

Continuous data will be summarized using the number of observations (n), mean, standard deviation (std), median, minimum, and maximum. Minima and maxima will be rounded to the precision of the original value, and means, medians, and 95% confidence intervals (CIs) if presented will be rounded to 1 decimal place greater than the precision of the original value. The std will be rounded to 2 decimal places greater than the precision of the original value, up to a maximum of 3 decimal places.

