6.1.2 Unscheduled visits

Unscheduled visit measurements of laboratory data, vital signs, and ECG will be used for computation of baseline and worst values and/or grades. Re-windowing for unscheduled visits will not be performed.

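### SAP 4.9.3: the ECG change-by-visit summary has no scheduled post-baseline data, and the QTcF table's rows do not show how many patients were tested

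*SAP*

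**What the plan says.** **Schedule.** Protocol 7.4.7 states: "One 12-lead electrocardiogram (ECG) will be performed at screening as per SoE". The ECG row of the Schedule of Events (Protocol Table 2) has a single mark, at screening. Anything later is discretionary: "Additional ECG assessments may be performed as clinically indicated".

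**By-visit summary.** SAP 4.9.3 plans descriptive statistics for the ECG values and "for their changes from baseline at each scheduled assessment".

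**QTcF table.** SAP 4.9.3 continues: "The following abnormal QTcF will be reported by a frequency table". It names three absolute categories at any post-baseline time (above 450 to 480 ms, above 480 to 500 ms, above 500 ms) and two change categories (above 30 to 60 ms, above 60 ms). No row is given for normal values, for number tested or for not tested.

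**Use of unscheduled ECGs.** Protocol 9.8.3 puts unscheduled data into worst-case summaries, "which will capture a worst case across all scheduled and unscheduled visits after the first dose of study drug". SAP 6.1.2 agrees: "Unscheduled visit measurements of laboratory data, vital signs, and ECG will be used for computation of baseline and worst values and/or grades". It adds that unscheduled visits are not re-windowed.

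**Denominator.** SAP section 4 (Statistical Methods) presents categorical data "with the number of patients in the analysis population as the denominator for percentages". SAP 4.9 makes the all-treated population the default for safety. SAP 3.2 gives 41 treated patients in total, without the split by cohort. On zero counts, SAP section 4 says: "Percentages will be rounded to 1 decimal place and not be displayed for zero counts".

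**The concern.** Two features of SAP 4.9.3 do not fit the ECG schedule.

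First, a change from baseline by scheduled assessment needs a scheduled assessment after baseline, and there is none for ECG. The same sentence is used in SAP 4.9.4 and 4.9.5 for vital signs and ECOG, which do have scheduled visits on treatment.

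Second, the QTcF table can be filled only by patients whose investigator had a reason to order an ECG. Dividing by all treated patients puts everyone without a post-baseline QTcF on the not-abnormal side. As every specified row is an abnormal category, a reader cannot recover the number tested from those rows. A low percentage could mean that few patients had a long QTcF, or that few were looked at.

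Cohort B admits some patients because of cardiac comorbidity, and the SAP introduction says the study was stopped with the benefit-risk profile given as the reason. Descriptive safety is a large part of what remains to be reported. No efficacy result is involved.

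**Working it through.** The plan gives no figure of its own on this point, so the check sets the sections side by side and then works through the denominator rule.

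**Step 1: by-visit change summary.**
- Scheduled ECGs per patient: 1, at screening (Protocol Table 2 and 7.4.7).
- Baseline: the last value up to the first dose (SAP 4.9), so the screening ECG is normally the baseline itself.
- Scheduled ECGs after the first dose: 0.
- Unscheduled ECGs cannot fill the visits, because SAP 6.1.2 does not re-window them.

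The by-visit change summary therefore has n = 0. The summary of screening values is valid.

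**Step 2: denominator of the QTcF table.** Let N be the number treated, m the number with a post-baseline QTcF, and x the number in an abnormal category. N = 41 pooled (SAP 3.2); if shown by cohort, N is the cohort size. Neither m nor x is in the documents; both are assumptions, shown over a range.

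- Percentage under the SAP rule: x/N.
- Share of tested patients: x/m.
- Identity: x/N = (x/m) × (m/N).

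With x = 2 assumed:

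| m (assumed) | m/N | SAP rule, x/N | Tested patients, x/m |
|---|---|---|---|
| 8 | 8/41 = 0.195 | 2/41 = 4.9% | 2/8 = 25.0% |
| 20 | 20/41 = 0.488 | 2/41 = 4.9% | 2/20 = 10.0% |
| 30 | 30/41 = 0.732 | 2/41 = 4.9% | 2/30 = 6.7% |
| 41 | 41/41 = 1.000 | 2/41 = 4.9% | 2/41 = 4.9% |

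Check: 25.0% × 0.195 = 4.9%, and 10.0% × 0.488 = 4.9%. The printed figure is the same in all four cases. If m = 41, the two rules agree.

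**Step 3: zero counts.** With x = 0, the row shows 0 and no percentage. It looks the same for every m from 0 to 41.

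**Step 4: can m be recovered from the specified rows?** There are 3 absolute rows and 2 change rows, all abnormal. With one category per patient, the absolute block adds up to x, not to m. SAP 4.9.3 does not say that each patient is counted once; without that rule, a patient with ECGs in two ranges could appear in two rows.

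**Step 5: do the blocks reconcile once normal rows and separate denominators are added?** The numbers are assumed for illustration.
- Absolute block, 20 patients with a post-baseline QTcF, 2 of them abnormal: 18 at or below 450 ms + 2 above = 20; 20 + 21 without a post-baseline QTcF = 41.
- Change block, 18 patients with both a baseline and a post-baseline QTcF, 1 of them with an increase above 30 ms: 17 + 1 = 18; 18 + 23 without such a pair = 41.

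The two blocks need their own denominators, because a patient may have a post-baseline QTcF but no baseline QTcF.

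**The case against.** The strongest reply is that nothing false would be reported. The share of treated patients with a documented abnormal QTcF is a valid description, and it follows the SAP's general rule. An empty change summary produces no wrong number. ECG is not named in the secondary endpoint on changes from baseline. All ECG data are listed for 41 patients, so the number tested can be counted by hand. Protocol 8.1.3 requires abnormal assessments that need intervention, or that change study treatment, to be recorded as adverse events. Table shells are not in the documents and might show the number tested. Finally, a tested-only denominator is selected by clinical indication and is no estimate of incidence.

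Most of this stands, and it keeps the point small. It does not remove it. The denominator is a stated rule rather than a gap, and SAP 4.9.3 makes no exception for a measurement that most patients may not have had. The protocol divides by the number tested where testing defines the result: Protocol 9.10 does so for anti-drug antibodies. The selection objection is met by a footnote.

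Any repair must also be exact. SAP 4.9.3 reports ECG parameters as the sites provide them and derives none, so a patient can have a post-baseline ECG without a QTcF. The untested line must count missing QTcF values, not missing ECGs.

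**Conclusion.** The point holds as a minor reporting weakness, at the low end. The by-visit ECG change summary has no scheduled data; removing it is housekeeping. The QTcF table is sound in kind, but its stated denominator and rows leave the number tested unseen. The size is unknown, because the number tested is not given; the effect is nil if all 41 patients had a post-baseline QTcF. The conclusion assumes that the table follows the SAP text and that the shells add nothing.

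Three stronger readings are not supported:

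- A reader might infer that the QTcF table is void because no post-baseline ECG is scheduled. Protocol 9.8.3 and SAP 6.1.2 both provide for unscheduled ECGs in worst-case summaries.
- A reader might infer that the table understates the true rate of QTcF prolongation by a known factor. The number tested is unknown, and the tested-only share is itself selected, so it is not the true rate.
- A reader might infer a broken commitment on LVEF, which the Schedule of Events shows after screening but for which the SAP names no output. Protocol 9.8.3 promises no LVEF summary, and SAP section 1 says that not all protocol analyses are covered. LVEF is not part of this point.

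**What to change.** Change SAP 4.9.3 as follows.

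1. **By-visit summary.** Limit it to the screening values and remove the change from baseline by visit.
2. **Absolute QTcF block.** Let m1 be the patients with at least one post-baseline QTcF. Assign each patient to one category by the maximum post-baseline value. Add a row for 450 ms or below. Show x/m1. Give N − m1 on a separate line, as patients with no post-baseline QTcF.
3. **Change block.** Let m2 be the patients with both a baseline and at least one post-baseline QTcF. Assign each patient to one category by the largest increase. Add a row for a change of 30 ms or less. Show x/m2. Give N − m2 on a separate line, as patients without a baseline and post-baseline pair.
4. **Presentation.** Show both blocks by cohort and overall. State in SAP 4.9.3 that these denominators replace the general rule in SAP section 4 for this table.
5. **Footnote.** Say that these ECGs were unscheduled and clinically indicated, so the percentages describe tested patients and do not estimate incidence in all treated patients.

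The cost is SAP wording, two category rows (five become seven), the count lines and one footnote, all from data already collected. The downside is that the percentages rest on smaller, selected denominators, which is why the footnote is needed.

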4.9.4 Vital Signs

Descriptive statistics (mean, standard deviation, median, and range) for vital signs data, including systolic and diastolic blood pressure, heart rate, respiration rate, and body temperature will be calculated for the raw data and for their changes from baseline at each scheduled assessment.

All vital signs data will be listed together with body weight.

4.9.5 ECOG Performance Status

Descriptive statistics (mean, standard deviation, median and range) will be calculated for the raw data and for their changes from baseline at each scheduled assessment.

ECOG performance score data will be listed.

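### The SAP leaves out the protocol's worst-case summary of ECOG performance status without declaring it, so no planned table counts the patients who worsened

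*SAP*

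**What the plan says.** **Protocol.** Change from baseline in ECOG PS is part of a named secondary endpoint (Section 3, Table 3). Section 9.8.3 lists the variables it covers: "The results of scheduled assessments of vital signs, physical examinations, ECOG performance status, and 12-lead ECGs will be summarized". It then sends unscheduled data into worst-case summaries, "which will capture a worst case across all scheduled and unscheduled visits after the first dose of study drug", and leaves further detail to the SAP.

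**SAP, on ECOG PS.** Section 4.9.5 has two sentences. The first is "Descriptive statistics (mean, standard deviation, median and range) will be calculated for the raw data and for their changes from baseline at each scheduled assessment". Next comes "ECOG performance score data will be listed". There is no frequency, shift or worst-grade table.

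**SAP, on unscheduled visits.** Section 6.1.2 reads "Unscheduled visit measurements of laboratory data, vital signs, and ECG will be used for computation of baseline and worst values and/or grades". ECOG PS is not among the data types named.

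**SAP, on departures from the protocol.** The whole of section 3.4 is "Not applicable". Section 1 says in general terms that, because the study was discontinued, some protocol analyses are not covered. Section 2.2 gives PFS, OS and patient-reported outcomes as examples of what is dropped for lack of follow-up. Neither section mentions ECOG PS.

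**The concern.** ECOG PS is a set of ordered descriptive grades (Protocol Appendix 12.1). The natural safety question is how many patients lost function on treatment, and by how much. Means and SDs at each visit do not answer it: one patient's gain offsets another's loss, and each visit's figures describe only the patients assessed at that visit. The protocol's worst-case summary would come closer to an answer, because it takes one worst value per patient and admits unscheduled visits.

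The patients are unfit, frail or have cardiac disease. SAP 1 gives an unfavourable benefit-risk profile as part of the reason for stopping. A count of patients with functional decline therefore belongs in the final report.

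Unscheduled values carry extra weight here. As far as the extracted table can be read, the Schedule of Events marks ECOG PS at screening, on Day 1 of Cycles 1, 2 and 3, and at end of treatment, with nothing in Cycles 4-6. For a patient treated through Cycle 6, a decline in those cycles would be recorded only at end of treatment or at an unscheduled visit.

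**Working it through.** The plan states no figure for this point, so there is none to reproduce. The check is a comparison of texts, followed by an illustration of the consequence.

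**Step 1. Protocol against SAP**

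| Item | Protocol | SAP |
|---|---|---|
| ECOG PS summary at scheduled visits | Required (9.8.3) | Planned (4.9.5) |
| ECOG PS worst case, scheduled plus unscheduled | Required (9.8.3) | Absent from 4.9.5; ECOG PS not named in 6.1.2 |
| Laboratory worst case | Required (9.8.2) | Kept (4.9.2): "which will capture a worst case across all scheduled and unscheduled visits after the first dose of study treatment" |
| ECG, any post-baseline | Worst case required (9.8.3) | QTcF frequency table (4.9.3) |
| Declared modification | – | None (3.4) |

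The SAP keeps this kind of output for laboratory data and ECG but not for ECOG PS. Its own general rule in section 4 is counts and percentages for categorical data, and 4.9.5 does not apply that rule.

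**Step 2. Can the planned statistics show how many patients declined?**

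Inputs: n = 41 treated patients (SAP 3.2). The changes are assumed; a positive change is worse.

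- Set A: 7 patients at +2, 14 at -1, 20 at 0.
- Set B: 1 patient at +2, 18 at +1, 20 at -1, 2 at 0.

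Mean = sum of changes / 41.
- A: (7×2 - 14×1)/41 = 0.0
- B: (1×2 + 18×1 - 20×1)/41 = 0.0

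SD = √(sum of squared changes / 40), since both means are zero.
- A: √((7×4 + 14×1)/40) = √(42/40) = 1.025
- B: √((1×4 + 18×1 + 20×1)/40) = √(42/40) = 1.025

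Median = 21st ordered value.
- A: the 15th to 34th values are 0, so the median is 0.
- B: the 21st and 22nd values are 0, so the median is 0.

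Range: -1 to +2 in both.

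Decline of 2 or more grades: A has 7/41 = 17.1%; B has 1/41 = 2.4%.

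If all 41 patients are further assumed to start at grade 1, each raw grade is 1 plus the change. The raw statistics then also coincide: mean 1.0, SD 1.025, median 1, range 0 to 3.

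**Step 3. Range of the illustration**

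The same construction (k patients at +2 and 2k at -1, against 1 at +2, 3k-3 at +1 and 3k-1 at -1, the rest at 0) gives matching statistics for k = 2 to 7. The contrast runs from 2/41 (4.9%) against 1/41 up to 7/41 (17.1%) against 1/41. The documents do not give the cohort split. For an assumed cohort of 20 and k = 3, both sets give mean 0.0, SD √(18/19) = 0.973, median 0 and range -1 to +2, with 3/20 (15.0%) against 1/20 (5.0%) declining by 2 grades.

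**Step 4. Unscheduled values**

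SAP 4.9.5 restricts its statistics to scheduled assessments, and 6.1.2 does not bring in unscheduled ECOG values. A decline seen only at an unscheduled visit therefore appears in the listing and in no ECOG summary table.

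**The case against.** The strongest reply is that nothing is hidden. Section 4.9.5 includes the median and the range, for raw grades and for changes. In the illustration the table would show a maximum change of +2, and the listing keeps every value. With 41 patients a reader could count from the listing. Clinically significant worsening is also reportable as an adverse event (Protocol 8.2), and adverse events are summarised by grade. This stands against any claim that severe decline would go unseen. It does not supply the count. The range at each visit says that at least one patient declined, not how many, and ranges from different visits cannot be combined into a number of patients. A hand count from a listing does not replace a summary that the protocol promised.

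A second reply is that SAP 1 discloses a reduced scope after early termination. That disclosure is general. ECOG PS is still analysed, and a worst post-baseline grade needs no long follow-up, so the sentence does not explain this omission.

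Third, ECOG PS is not alone: SAP 4.9.4 describes no worst-case table for vital signs, and SAP 4.9.6 only lists physical examinations, although Protocol 9.8.3 covers both. This is correct. It is a reason to check those sections too, not to leave this one.

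Fourth, the protocol asks for a worst-case summary of ECOG PS, not specifically for a shift table. This is also correct. The shift layout is proposed because it meets the requirement and gives the count in one table.

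A reader might also infer that patients who enter at ECOG 2-3 can only hold or improve, which would bias the mean towards benefit. The documents do not support this. The scale in Appendix 12.1 runs on to grades 4 and 5, and the reversibility condition in inclusion criterion 5 applies only to grade 3.

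**Conclusion.** The point holds as an undeclared gap between protocol and SAP with a practical consequence. The required worst-case summary of ECOG PS is missing, no planned table gives the number or percentage of patients who worsened, and post-baseline values from unscheduled visits reach no summary table. It should be put right, but it concerns one item within a secondary safety endpoint and does not affect the primary endpoints.

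The size in this trial cannot be stated, because the documents contain no ECOG data. The contrast of 17.1% with 2.4% shows only that the planned statistics can fail to separate very different outcomes; it is not an estimate. The remark about Cycles 4-6 rests on a table read from broken text. If that gap is real, it is a feature of data collection that an SAP change cannot repair; the change can only make use of whatever unscheduled values exist.

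Two stronger conclusions are not supported: that severe decline would be invisible in the report, and that the by-visit statistics should be removed. They describe change over time and need a supplement.

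**What to change.** - **SAP 4.9.5:** keep the by-visit summary. Add one table, by cohort, of baseline grade against worst post-baseline grade, using scheduled and unscheduled visits after the first dose. In the same table give counts and percentages of patients worsening by 1 grade and by 2 or more grades, and the number with no post-baseline assessment.
- **SAP 6.1.2:** add ECOG PS to the data types whose unscheduled values count towards worst values.
- **If the sponsor prefers not to produce the table:** record the omission and the reason in SAP 3.4 in place of the present entry.

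The cost is a few lines of SAP text and the programming of one extra table. It needs no new data and alters no other analysis.

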4.9.6 Physical Examinations

Listing of physical examinations will be provided.

4.9.7 Pregnancy Test

Listing of pregnancy test, if applicable, will be provided.

5 Data handling conventions

6.1 General conventions

6.1.1 Missing data

In general, imputation of missing dates will be made for AE onset date, AE resolution date, date of death, medication start/end dates, start and end dates of prior and subsequent therapies, and date of initial diagnosis for reporting. No imputation should be done at the data level.

- If dates are completely missing, no imputation will be made.
- For any partial date with missing year, no imputation will be made.
- For missing initial diagnosis date, if only day is missing, then the first day of the month will be used; if only year is present, then Jan 1st will be used. If such imputed date for initial diagnosis is on or after date of first dose, then date of first dose - 1 will be used.
- If the imputed date is for an AE start date and is in the same year and month as but before the first dose date, then the first dose date will be used, or if the imputed AE start date is after the AE end date, then the AE end date will be used. If the imputed date is for an AE start date and is in the same year and month as but after the last dose date + 15 weeks, then the last dose date + 15 weeks will be used.
- If a medication date or time is missing or partially missing, so it cannot be determined whether it was taken prior or concomitantly, it will be considered as a prior and concomitant medication.
- If the imputed date is for a date of death and is before the last date that the patient is known to be alive, the latter date will be used.
- If the date part is missing for new anticancer therapy, the month and year will be used for comparison with disease assessment.

Handling of missing relationship to investigational product of TEAEs

If the assessment of the relationship to IP is missing, then the relationship to IP has to be assumed and the TEAE considered as such in the frequency tables of possibly related TEAEs, but no imputation should be done at the data level.

Handling of missing severity/grades of AEs

If the severity/grade is missing for one of the treatment emergent occurrences of an AE, the maximal severity of the remaining occurrences will be considered. If the severity is missing for all the occurrences a “missing” category will be added in summary table.

No other imputation of values for missing data will be performed.

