8.3 Assessment of Severity

The AEs will be graded according to Common Terminology Criteria for Adverse Events (CTCAE) v5.0. For events not included in the CTCAE criteria, the severity of the AE is graded on a scale of 1 to 5 as shown in [Table 6](#).

Table 6 **Definition of Severity Grades for CTCAE**

Grade	Definition
1	Mild; asymptomatic or mild symptoms; clinical or diagnostic observations only; intervention not indicated.
2	Moderate; minimal, local or noninvasive intervention indicated; limiting age appropriate instrumental activities of daily living (ADL). ^a
3	Severe or medically significant but not immediately life threatening; hospitalization or prolongation of hospitalization indicated; disabling; limiting self-care ADL. ^b
4	Life-threatening consequences; urgent intervention indicated.
5	Death related to adverse event.

^a ADL refers to preparing meals, shopping for groceries or clothes, using the telephone, managing money, etc.

^b Self-care ADL refers to bathing, dressing and undressing, feeding self, using the toilet, taking medications, and not bedridden.

The AEs characterized as intermittent do not require documentation of onset and duration of each episode.

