4.9.1 Adverse Events, Serious Adverse Events, and Deaths

4.9.1.1 Analyses of Adverse Events

An AE is defined as any untoward medical occurrence in a patient or clinical investigation subject administered a pharmaceutical product, which does not necessarily have to have a causal relationship with this study treatment.

A treatment-emergent AE (TEAE) is defined as an AE that occurs or worsens in the period extending from the first dose of study drug to 15 weeks after the last dose of study drugs in this study (either loncastuximab or Rituximab) or start of a new anticancer therapy, whichever is earlier. The primary focus of adverse event reporting will be on TEAEs.

AEs will be coded according to MedDRA Version 24.1, and the severity of the toxicities will be graded according to the National Cancer Institute (NCI) Common Terminology Criteria for Adverse Events (CTCAE) Version 5.0, where applicable.

The summary of overall TEAEs includes:

- TEAEs
- Drug-related TEAEs (loncastuximab tesirine or Rituximab)
- Grade ≥ 3 TEAEs
- Drug-related Grade ≥ 3 TEAEs (loncastuximab tesirine or Rituximab)
- Serious Adverse Events (SAEs)

- TEAEs leading to dose delayed, reduced or interrupted (loncastuximab tesirine or Rituximab)
- TEAEs leading to discontinuation of loncastuximab tesirine or Rituximab
- TEAEs leading to death
- Infusion related reaction

The incidence of TEAEs will be summarized by system organ class (SOC) and preferred term (PT). A patient will be counted only once within a SOC and PT, even if the patient experienced more than one AE within a specific SOC and PT.

- All TEAEs \geq Grade 3 by PT, showing number (%) of patients with at least one TEAE, sorted by decreasing incidence of PTs
- All TEAEs by primary System Organ Class (SOC) and PT, showing number (%) of patients with at least one TEAE, sorted by SOC in alphabetic agreed order and decreasing incidence of PTs within SOC. This sorting order will be applied to all other tables, unless otherwise specified.
- All TEAEs by primary SOC, PT and Maximal CTCAE grade, showing number (%) of patients with at least one TEAE, sorted by SOC and PT in alphabetic order. This sorting order will be applied to all other tables, unless otherwise specified.
- All TEAEs \geq Grade 3 by primary SOC, PT and Maximal CTCAE grade
- All related TEAEs by primary SOC, PT and Maximal CTCAE grade (including possibly related, probably related, or related)

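### SAP 6.1.1 leaves a fatal or life-threatening TEAE with a blank grade out of the Grade ≥ 3 tables unless another occurrence of that AE is itself Grade ≥ 3

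*SAP*

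**What the plan says.** SAP 6.1.1 (Missing data) has two adjacent rules for incomplete AE records.

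- **Missing grade.** "If the severity/grade is missing for one of the treatment emergent occurrences of an AE, the maximal severity of the remaining occurrences will be considered". The next case begins "If the severity is missing for all the occurrences" and sends the AE to a separate missing category in the summary table.
- **Missing causality.** "then the relationship to IP has to be assumed and the TEAE considered as such in the frequency tables of possibly related TEAEs". The AE counts as related.

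The section ends: "No other imputation of values for missing data will be performed". No rule lets a fatal outcome or a seriousness criterion supply a grade.

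SAP 4.9.1.1 lists the outputs that depend on these rules. They include overall rows for Grade ≥ 3 TEAEs and for "Drug-related Grade ≥ 3 TEAEs (loncastuximab tesirine or Rituximab"), tables of Grade ≥ 3 TEAEs, and separate tables of fatal and of serious TEAEs by maximal grade.

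Protocol 8.2 has severity, seriousness and outcome recorded for every AE. In Protocol 8.3, Table 6 puts death related to the AE at Grade 5 and life-threatening consequences at Grade 4. Protocol 9.8.1 counts a patient once per Preferred Term, at the worst grade.

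**The concern.** The study collects what is needed to grade the most serious ungraded events, and the SAP does not use it. Two problems follow.

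First, outputs can disagree. A TEAE selected for the fatal table by its outcome can appear there with grade missing and be absent from the Grade ≥ 3 tables.

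Second, the rule can work against Protocol 9.8.1. If the ungraded occurrence was the worst one, the patient is reported at the milder grade of another occurrence.

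The neighbouring causality rule takes the cautious direction for a blank field, and no reason is given for treating a blank grade differently. Grade ≥ 3 TEAEs are a headline safety summary, and with 41 treated patients one misclassified patient visibly moves a percentage.

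**Working it through.** The plan gives no figure on this point, so there is none to reproduce.

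**1. The rules applied to single cases (one AE term in one patient)**

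| Occurrences | Grade under SAP 6.1.1 | Grade by Table 6 | In Grade ≥ 3 tables for that AE? |
|---|---|---|---|
| One, fatal, grade blank | missing | 5 | No |
| Grade 1, then life-threatening with grade blank | 1 | 4 | No |
| Grade 3, then fatal with grade blank | 3 | 5 | Yes, but at the wrong maximal grade |
| One, Grade 3, causality blank | 3 | 3 | Yes, and counted as related |

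The third row shows that an ungraded AE is not always lost. The fourth shows that the drug-related row can be raised.

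**2. Direction of error**

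Take one AE per patient. Let p3 be the probability of Grade ≥ 3, pr the probability of being related, and mg and mc the proportions with missing grade and missing causality, all independent. None of these is in the documents; all are assumptions.

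- Overall Grade ≥ 3: true rate p3, reported rate p3 × (1 − mg). This is never above p3. With p3 = 0.5, the reported rate is 0.5 × 0.98 = 49.0% at mg = 2% and 0.5 × 0.95 = 47.5% at mg = 5%.
- Drug-related Grade ≥ 3: true rate p3 × pr, reported rate p3 × (1 − mg) × [pr + (1 − pr) × mc].
  - p3 = 0.5, pr = 0.3, mg = 2%, mc = 5%: true 15.0%; reported 0.5 × 0.98 × (0.3 + 0.7 × 0.05) = 16.4%, which is 1.4 points too high.
  - p3 = 0.5, pr = 0.7, mg = 5%, mc = 2%: true 35.0%; reported 0.5 × 0.95 × (0.7 + 0.3 × 0.02) = 33.5%, which is 1.5 points too low.

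**3. The same question for 41 patients**

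This simulation used 4,000 runs with four AE records per patient, each with probability 0.25 of Grade ≥ 3 and 0.5 of being related (assumed). It compares the number of patients counted with the true number.

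| Missing grade | Missing causality | Grade ≥ 3 count low / high | Related Grade ≥ 3 count low / high |
|---|---|---|---|
| 2% | 0% | 29% / 0% of runs | 25% / 0% |
| 0% | 2% | 0% / 0% | 0% / 23% |
| 2% | 2% | 29% / 0% | 19% / 18% |
| 5% | 5% | 59% / 0% | 32% / 29% |

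The overall count is never too high. The related count goes both ways.

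**4. Size**

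SAP 3.2 gives 41 treated patients. A patient is lost from the overall Grade ≥ 3 row only if no other TEAE of theirs is recorded as Grade ≥ 3. Each such patient is worth 1/41 = 2.4 points; two are worth 2/41 = 4.9 and three 3/41 = 7.3. The number of such patients is unknown and may be zero. The documents give no split of the 41 by cohort, so no cohort figure can be calculated.

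**The case against.** The strongest case against is that the gap is hypothetical and the events are visible anyway. Severity is a specified item on the AE page (Protocol 8.2), monitors check completeness (Protocol 10.5), and nothing in the documents shows a missing grade. Fatal TEAEs are selected by outcome and serious TEAEs by seriousness, each with its own table. Deaths are also tabulated and listed, and all AEs are listed. An open missing category may be more honest than a guessed grade, and causality and grade need not follow one rule. All of this stands: it limits the harm to misclassification and keeps the point minor. It does not correct the Grade ≥ 3 count.

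A second objection is that Protocol 8.3 applies the Table 6 scale to events without their own CTCAE criteria, and that seriousness is not severity. This holds against a broad mapping. Table 6 lists "hospitalization or prolongation of hospitalization indicated" among several Grade 3 descriptors, which is not the same as an admission that meets the SAE definition, so grading every hospitalization as 3 is debatable. Counting every remaining ungraded AE as Grade 3 would turn mild events into severe ones. The objection is weak against the top two grades: Table 6 is titled as the CTCAE grade definitions, and a fatal AE is Grade 5 by that definition.

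A reader might also infer three stronger things that the documents do not support:

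- *That the drug-related Grade ≥ 3 rate can only err low.* The causality rule, "then the relationship to IP has to be assumed", pushes that row up, so the net direction is undetermined.
- *That an ungraded AE can never count as Grade ≥ 3.* The patient is counted for that AE when another occurrence is Grade ≥ 3. If the rule is read as giving the ungraded occurrence that maximum, a related ungraded occurrence could even take its grade from an unrelated one.
- *That the rule coloured the benefit-risk judgement behind the stop.* SAP Section 1 reports the decision of 20 July 2023 as already made, so this SAP did not inform it.

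**Conclusion.** The point holds in a narrow form. SAP 6.1.1 gives an ungraded occurrence no grade of its own, even where the recorded outcome or seriousness fixes one under Protocol Table 6. A fatal or life-threatening TEAE with a blank grade, and no other Grade ≥ 3 occurrence of that AE, is therefore missing from the Grade ≥ 3 tables.

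The statement that the error can only be downward applies to the overall Grade ≥ 3 TEAE rate and to this rule alone. The date rules in the same section can add TEAEs of any grade, because some partial start dates are moved into the treatment-emergent window.

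The size is 2.4 points per affected patient out of 41, for an unknown number of patients. Importance is low: safety is descriptive and the events appear elsewhere. The remedy costs almost nothing.

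**What to change.** Add to the missing-grade paragraph of SAP 6.1.1: a TEAE with missing grade is tabulated as Grade 5 if its outcome is fatal, and as Grade 4 if its seriousness criterion is life-threatening. Apply this before the maximum over occurrences is taken, so that a milder graded episode cannot stand in for it. Footnote the number so assigned in each affected table, and leave the data unchanged, as the SAP already does for causality.

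Keep all other ungraded AEs in the missing category. A footnoted sensitivity count treating them as Grade 3 is optional.

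The cost is a couple of sentences and a small programming step. Outcome and seriousness are already recorded; the fix assumes that the specific seriousness criterion is recorded too, which should be checked against the CRF. The downside is that the Grade ≥ 3 rate may become slightly less favourable. If no fatal or life-threatening TEAE lacks a grade, no result changes.
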